3.7.3 General supportive guidelines

3.7.3.1 Dose Modification for General Toxicities

General guidelines regarding management and dose reduction for adverse events that are considered by the investigator to be related to study treatment and for which specific guidelines do not apply are provided in [Table 3-3](#). These guidelines are intended primarily for toxicities not easily managed with routine supportive care. For example, alopecia is not an indication for dose modification, nor is grade 2 nausea and vomiting that can be easily managed with antiemetics.

These are general guidelines and investigators should always use clinical judgment in determining dose adjustments for any individual patient. Some toxicities may require hospitalization for stabilization, additional work-up, and consultation with a specialist before treatment can be restarted.

Investigators should always err on the side of caution in these settings if treatment-related toxicity is a possibility. Note that guidelines for management of hepatobiliary adverse events

are provided separately in [Section 3.7.8](#). Additionally, please refer to the SPM for additional dose modification guidance.

Table 3-3 Dose Modification Guidelines - General

CTCAE Grade	Action and Dose Modification ^{a,b}
Grade 1 or Grade 2 (tolerable)	Continue study treatments at same dose level (no dose modification) and monitor as clinically indicated
Grade 2 (Intolerable) or Grade 3	
1st, 2nd, or 3rd occurrence	Interrupt study treatments until toxicity resolves to \leq grade 1 then restart at next lower dose level
4th or greater occurrence	Discontinue treatment.
Grade 4	
1st occurrence	Interrupt study treatments until toxicity resolves to \leq grade 1 or baseline then restart at next lower dose level or discontinue at discretion of investigator
All other occurrences	Discontinue treatments

^{a.} Treatments should be discontinued if more than 3 dose reductions are required.

^{b.} Approval from the Novartis Medical Lead is required to restart study treatments after ≥ 21 days interruption

When an individual's adverse reactions are under effective management, dose re-escalation following the same dosing steps as de-escalation may be considered.

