The protocol is also being amended to add updated RANO criteria specifically for low grade glioma (RANO-LGG; Wen 2017) as the basis for independent review. These more recent RANO-LGG criteria allow for the identification of measurable target lesions in patients with LGG that may not be gadolinium enhancing and are best seen by T2/FLAIR imaging sequences. These updated RANO - LGG criteria will be utilized in supplemental independent RANO response determination for those patients with LGG. Note that the independent response determinations that were originally intended to be applied using the older RANO criteria will be retained for analysis purposes. Also note that the response category of 'minor response' will not be used in this trial.

Changes in the protocol:

Changes to specific sections of the protocol are shown in the track changes version of the protocol using strikethrough red font for deletions and red underline for insertions:

- List of Abbreviations Table: updated to include PIP and RANO.
- Removal of named contact details and integrated signature pages in alignment with current Novartis template and standards.
- Section 3.1.2: Amended to match the clinical measures in the current approved PIP.

- Appendix 15.2: Added updated RANO criteria for LGG patients (RANO-LGG) and removed the minor response category in the “Response assessment of target lesions” table as it is not used in this clinical trial.

IRBs/IECs

A copy of this amended protocol will be sent to the Institutional Review Board (IRBs)/Independent Ethics Committee (IECs) and Health Authorities.

The changes described in this amended protocol require IRB/IEC approval prior to implementation.

Amendment 10 (04-Apr-2019)

Amendment Rationale

As of 06-Feb-2019, 85 patients have received study treatment in 8 countries; Part 1 dose escalation has enrolled 27 patients and is closed to enrollment. Based on the data from these 27 subjects, no maximum tolerated dose was established in this pediatric population and the recommended Phase 2 doses (RP2Ds) for dabrafenib monotherapy were determined based on exposure target as 5.25 mg/kg/day for patients < 12 years old and 4.5 mg/kg/day for patients ≥ 12 years old, divided into two equal daily doses, and not to exceed adult dose.

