3.1.1 Part 1 – Dose Escalation

Part 1 is a repeat dose, dose escalation study. The RSD (Skolnik, 2008) builds on the classic 3+3 design, but allows for continued recruitment of subjects while the data from the first 3 subjects in each cohort is collected (up to 6 subjects per cohort). For dose escalation decisions, all available data are used to inform the decision. The starting dose will be 3 mg/kg with dose levels for subsequent dose levels (+1 and +2 Dose Levels) as outlined in Table 3-1.

Table 3-1 Dabrafenib Dose Levels ^a

Dose Level	Total Daily Dose (mg/kg) ^c
-2 Dose Level	1.5 mg/kg
-1 Dose Level	2.25 mg/kg
Starting Dose Level ^b	3 mg/kg
+1 Dose Level	3.75 mg/kg
+2 Dose Level	4.5 mg/kg
+3 Dose Level	5.25 mg/kg
+4 Dose Level	6.0 mg/kg

^a Intermediate and additional dose levels may be explored based on emerging PK and safety data.

^b Starting dose level. The first cohort of subjects will receive approximately 80% of the adult mg/kg dose (doses will be rounded based on the smallest 10mg capsule increments for subjects receiving capsules). The adult dose is 3.75 mg/kg given as 2 divided doses.

^c The total daily dose will be split evenly into a morning and evening dose (BID dosing). The total daily dose will not exceed 300 mg (150 mg BID).

The actual weight-adjusted dose to be administered for a given dose level may be adjusted based on safety, tolerability and preliminary PK data at previous dose levels; these dose adjustments may involve either an increase or a decrease in the planned dose for a given dose level. Dosing frequency may also be adjusted based on emerging PK and/or safety data. Cohorts may be added in order to evaluate additional dose levels. The study procedures for these additional subject(s) or cohort(s) will be the same as those described for other study subjects.

Up to 6 subjects can be enrolled concurrently at one dose level dependent upon the number of subjects enrolled at the current dose level, the number of subjects who have experienced a dose limiting toxicity (DLT, see Section 3.3) at the current dose level, and the number of subjects enrolled but with data pending at the current dose level. Dose escalation schematic is in Appendix 1.

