3.6 Investigational Product and Other Study Treatment Dosage/Administration

In France, children younger than 6 years and children 6 years and older with a risk of choking when swallowing capsules will be required to use the powder suspension formulation or the dispersible tablets.

Capsules: Dabrafenib capsules will be supplied by Novartis (for subjects able to reliably and consistently swallow capsules).

Powder for oral suspension: Dabrafenib will be supplied by Novartis as a powder for oral suspension contained in single-use foil laminated stickpacks. The powder will be constituted with a specified volume of water at the time of use to form an oral suspension of 10 mg/mL dabrafenib. Administration will be performed using appropriate-sized oral syringes (1 mL, 5 mL, or 20 mL) to enable adjustments in dosing volume for individualized doses. The constituted suspension is intended for immediate consumption and the unused portion of the suspension will be discarded. Supplies for constitution will be supplied by Novartis or its authorized agent. Detailed instructions for constitution and dosing will be provided in the SPM.

Dispersible tablets: Dabrafenib will be supplied by Novartis as dispersible tablets. The tablets will be dispersed with a specified volume of water at the time of use to form a dispersion. Administration will be performed using a dosing cup / PP oral liquid dispenser.

Detailed instructions for the dispersion of the tablets and dosing will be provided in the SPM.

Dabrafenib (applicable for all formulations) will be administered orally, twice daily based on weight at the appropriate study dose level. A dosing nomogram (supplied in the SPM) based on weight and dose level will be used to prescribe dabrafenib to minimize inter-subject dosing variability.

Investigational product details are provided in [Table 3-2](#).

Table 3-2 Investigational Product

Formulation description:	HPMC Dabrafenib capsules	Dabrafenib powder for oral suspension	Dabrafenib Dispersible Tablets for oral suspension
Dosage form:	Capsule	Powder for oral suspension	Dispersible Tablet
Unit dose strengths:	10 mg, 25 mg, 50 mg and 75 mg	150 mg (in stickpack) 10 mg/mL (as oral suspension)	10mg
Route/ Frequency:	Oral / BID	Oral / BID	Oral / BID

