3.7.4 Dose Modification Guidelines - Adverse Events of Special Interest

3.7.4.1 Pyrexia

Pyrexia has been observed in adult subjects receiving dabrafenib. In a minority of cases pyrexia was accompanied by symptoms such as severe chills/rigors, dehydration, and hypotension, which in some cases can lead to acute renal insufficiency. Serious non-infectious febrile events have been observed and typically occurred within the first month of therapy.

Subjects should be instructed on the importance of immediately reporting febrile episodes. Therapy with dabrafenib should be interrupted if the patient's temperature is $\geq 38.5^{\circ}\text{C}$ or 101.3° Fahrenheit. In the event of a fever, the subject should be instructed to take anti-pyretics (e.g. ibuprofen or acetaminophen/paracetamol as appropriate to control fever). The use of oral corticosteroids should be considered in those instances in which anti-pyretics are insufficient. In subjects experiencing pyrexia associated with rigors, severe chills, dehydration or hypotension, serum creatinine and other evidence of renal function (e.g. creatinine clearance, BUN) should be monitored carefully during and following severe events of pyrexia. Pyrexia accompanied by hypotension, dehydration requiring intravenous fluids, renal insufficiency and/or severe (\geq Grade 3) rigors/chills in the absence of an obvious infectious cause should be reported as a SAE.

Guidelines regarding management and dose reduction for pyrexia considered to be related to dabrafenib are provided in [Table 3-4](#).

Table 3-4 Mandatory Dose Modification and Recommended Clinical Management for Pyrexia

Occurrence ^{a,b}	Recommended adverse event management guidelines	Mandatory dose modification requirements
Any	
 ● Clinical evaluation for infection and hypersensitivity^c ● Laboratory (local lab) work-up^c ● Hydration as required^d 	
1st Event ^b :	
 ● Administer anti-pyretic treatment as clinically indicated and initiate prophylactic treatment if associated with rigors, renal failure, dehydration, or hypotension^e 	
 ● Interrupt dabrafenib ● Once pyrexia resolves to baseline, restart dabrafenib at the same dose level ● If fever was associated with dehydration, hypotension, or renal insufficiency, reduce dabrafenib to the next lower dose level. ^g

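### One-level toxicity reductions in Tables 3-3 and 3-4 can leave the dose unchanged where the 300 mg/day cap binds, and at some low weights through capsule rounding

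*Protocol*

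**What the plan says.** Protocol Section 3.1.1, Table 3-1, sets a ladder of total daily doses from 1.5 to 6.0 mg/kg in steps of 0.75 mg/kg. Its footnotes add three limits:

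- Cap: "The total daily dose will not exceed 300 mg (150 mg BID"). Section 3.6 repeats it.
- Split: "The total daily dose will be split evenly into a morning and evening dose (BID dosing").
- Rounding: "doses will be rounded based on the smallest 10mg capsule increments for subjects receiving capsules". Neither the direction nor the basis (per dose or per day) is given.

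The rationale for Amendment 10 gives the selected doses as "5.25 mg/kg/day for patients < 12 years old and 4.5 mg/kg/day for patients ≥ 12 years old", subject to the adult maximum.

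Toxicity reductions are written as steps on this ladder. Table 3-3 (Section 3.7.3.1, general guidance) says "then restart at next lower dose level". Table 3-4 (Section 3.7.4.1) has a column of mandatory requirements. For a first or second fever with dehydration, hypotension or renal insufficiency it says "reduce dabrafenib to the next lower dose level", and for later fevers it requires one level less. Table 3-5 (renal function) speaks of a reduced dose, not a level.

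Section 3.6 lists capsule strengths of "10 mg, 25 mg, 50 mg and 75 mg", a 10 mg/mL suspension measured by syringe, and a 10 mg dispersible tablet. It places the dosing nomogram in the SPM. SAP Section 2.4 summarizes dose reductions by pooled disease cohort, and dose intensity and relative dose intensity by age below 12 and 12 or over.

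**The concern.** A level is a mg/kg figure, but the patient takes milligrams. Once the cap binds at two adjacent levels, a site can follow Table 3-4 to the letter and restart the patient on the dose that preceded the event. No section of the supplied documents says that a reduction must lower the administered mg, or what a level step means when the cap or rounding absorbs it.

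Two things are at stake. The first is clinical: a mandatory response to complicated fever may not deliver the reduction it names. The second is analytic: if the data record a level change as a dose reduction, the summary in SAP Section 2.4 would count reductions that did not occur, and tolerability afterwards would be credited to a lower dose that was never given. Such a step could also use up one of the three reductions that Table 3-3 allows before discontinuation.

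**Working it through.** **Check of the plan's own figure.** Section 1.2.2 equates the adult 300 mg/day with 3.75 mg/kg/day at 80 kg and calls the 3 mg/kg starting dose about 80% of it. 300 / 80 = 3.75 and 3 / 3.75 = 0.80. Both reproduce.

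**Cap.** Daily dose = min(300, level × weight), so the cap binds from 300 / level: 57.1 kg at 5.25, 66.7 kg at 4.5, 80 kg at 3.75 and 100 kg at 3.0 mg/kg/day. A step is empty once the lower of its two levels is capped.

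Starting at 4.5 mg/kg/day, in mg/day:

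| Weight | 4.5 | 3.75 | 3.0 | First cut | First two cuts together |
|---|---|---|---|---|---|
| 70 kg | 300 | 262.5 | 210 | 12.5% | 30% |
| 75 kg | 300 | 281.25 | 225 | 6.3% | 25% |
| 80 kg | 300 | 300 | 240 | 0% | 20% |
| 90 kg | 300 | 300 | 270 | 0% | 10% |
| 100 kg | 300 | 300 | 300 | 0% | 0% |

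Nominal cuts are 0.75 / 4.5 = 16.7% for one step and 1.5 / 4.5 = 33.3% for two.

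Starting at 5.25 mg/kg/day, the nominal first cut is 0.75 / 5.25 = 14.3%. At 60 kg the dose goes from 300 to 270 mg (10%). From 66.7 kg it stays at 300 mg (0%).

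**Rounding.** One level is 0.75 / 2 = 0.375 mg/kg per dose. With 10 mg units per dose, a change is guaranteed only from 10 / 0.375 = 26.7 kg. Below that the result depends on the rule. I scanned 8 to 26.6 kg in 0.1 kg steps (187 weights) and counted those where adjacent levels give the same dose:

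| Assumed rule | 5.25 to 4.5 | 4.5 to 3.75 | 3.75 to 3.0 |
|---|---|---|---|
| Nearest 10 mg per dose | 36% | 39% | 32% |
| Nearest combination of the four capsule strengths per dose | 6% | 12% | 11% |
| Nearest 10 mg per day | 6% | 5% | 7% |
| Suspension, assumed 1 mg resolution | 0% | 0% | 0% |

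Under the second and third rules every tie lies at or below 12.3 kg. Example at 12 kg: 5.25 and 4.5 mg/kg/day give 31.5 and 27.0 mg per dose. Both round to 30 mg under the first rule; capsule combinations give 30 and 25 mg. These percentages are shares of an even grid of weights, not of patients.

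**The case against.** The strongest reply is that the deciding document is absent. Doses by weight and level come from the SPM nomogram, and Section 3.7.3.1 also points to the SPM for further dose-modification guidance. The nomogram may already settle the matter. That stands as a limit on confidence, but the protocol text still contains the collision.

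Several stronger readings are tempting, and the documents do not support them:

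- *The safety response does nothing.* Treatment is first interrupted until recovery, repeated events lead to discontinuation under Table 3-3, and Section 3.7 routes every dose adjustment through the sponsor's medical lead with the investigator. From 80 kg to below 100 kg the second step does lower the dose.
- *All the reductions are mandatory.* Table 3-3 is guidance that leaves room for clinical judgment. The mandatory level-based reductions are those for pyrexia.
- *Renal toxicity is equally exposed.* Table 3-5 requires a reduced dose, so restarting on the same mg would not satisfy it.
- *About a third of small children are affected.* That needs one particular rounding rule. The rounding note covers capsules only, and how dispersible tablets are rounded is not stated.
- *Dose-limiting toxicity (DLT) counts are distorted.* Reductions enter the DLT definition only in the first 28 days of Part 1, which is closed, and no maximum tolerated dose was established. Many such events would qualify by grade anyway.
- *The ladder is too short.* Only two levels lie below 3 mg/kg, but four and five lie below the selected 4.5 and 5.25 mg/kg, and a footnote to Table 3-1 permits added levels.

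It is also fair to say that no supplied text defines how a dose reduction is recorded. SAP Section 2.4 refers to an earlier SAP that is not among the documents, so miscounting is a risk, not an established fact.

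**Conclusion.** The cap contradiction holds on the protocol's own figures and needs no assumption beyond body weight. A one-level reduction is empty from 80 kg at 4.5 mg/kg/day and from 66.7 kg at 5.25 mg/kg/day, and it is weakened at lower weights once the higher level is capped. From 100 kg, two steps from 4.5 mg/kg/day are empty. This is more than missing detail: a stated mandatory rule can be followed exactly without producing a reduction.

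The rounding version is smaller and conditional. It arises only below 26.7 kg, at roughly 5% to 39% of weights from 8 to 26.6 kg depending on the assumed rule, and not with suspension.

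The number of patients affected is unknown, because no weight distribution is given and enrollment is closed. With the nomogram also unseen, the point deserves correction but does not support a claim that dose reduction fails generally in this trial.

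**What to change.** Reconcile Table 3-1 and its footnotes, Section 3.6, and Tables 3-3 and 3-4 with the SPM nomogram. Show the resulting mg per dose by weight band, level and formulation, with the rounding rule stated for capsules and for dispersible tablets. Flag each band where adjacent levels give the same dose, and have the sponsor's clinical team state what a one-level reduction means there. No dose or clinical rule is proposed here.

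In the data derivations and the exposure summaries of SAP Section 2.4, count a dose reduction only when the administered mg falls, and list separately any level change that left the mg unchanged.

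The cost is one table in the protocol or SPM and one derivation rule. No extra patients or visits are needed, and the recorded weights and doses would show how many patients were affected.

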3.7.4 Dose Modification Guidelines - Adverse Events of Special Interest

3.7.4.1 Pyrexia

Pyrexia has been observed in adult subjects receiving dabrafenib. In a minority of cases pyrexia was accompanied by symptoms such as severe chills/rigors, dehydration, and hypotension, which in some cases can lead to acute renal insufficiency. Serious non-infectious febrile events have been observed and typically occurred within the first month of therapy.

Subjects should be instructed on the importance of immediately reporting febrile episodes. Therapy with dabrafenib should be interrupted if the patient's temperature is $\geq 38.5^{\circ}\text{C}$ or 101.3° Fahrenheit. In the event of a fever, the subject should be instructed to take anti-pyretics (e.g. ibuprofen or acetaminophen/paracetamol as appropriate to control fever). The use of oral corticosteroids should be considered in those instances in which anti-pyretics are insufficient. In subjects experiencing pyrexia associated with rigors, severe chills, dehydration or hypotension, serum creatinine and other evidence of renal function (e.g. creatinine clearance, BUN) should be monitored carefully during and following severe events of pyrexia. Pyrexia accompanied by hypotension, dehydration requiring intravenous fluids, renal insufficiency and/or severe (\geq Grade 3) rigors/chills in the absence of an obvious infectious cause should be reported as a SAE.

Guidelines regarding management and dose reduction for pyrexia considered to be related to dabrafenib are provided in [Table 3-4](#).

Table 3-4 Mandatory Dose Modification and Recommended Clinical Management for Pyrexia

Occurrence ^{a,b}	Recommended adverse event management guidelines	Mandatory dose modification requirements
Any	
 ● Clinical evaluation for infection and hypersensitivity^c ● Laboratory (local lab) work-up^c ● Hydration as required^d 	
1st Event ^b :	
 ● Administer anti-pyretic treatment as clinically indicated and initiate prophylactic treatment if associated with rigors, renal failure, dehydration, or hypotension^e 	
 ● Interrupt dabrafenib ● Once pyrexia resolves to baseline, restart dabrafenib at the same dose level ● If fever was associated with dehydration, hypotension, or renal insufficiency, reduce dabrafenib to the next lower dose level. ^g
2nd Event ^e	
 ● Same as for 1st event, and ● Within 3 days of onset of pyrexia 
 ● Optimize anti-pyretic therapy ● Consider oral corticosteroids for at least 5 days or as clinically indicated^f 	
 ● Same as 1st event.
Subsequent Events:	
 ● Within 3 days of onset of pyrexia 
 ● Optimize oral corticosteroid dose as clinically indicated for recalcitrant pyrexia^f ● If corticosteroids have been tapered and pyrexia recurs, restart steroids 	
 ● Interrupt dabrafenib ● Once pyrexia resolves to baseline, restart dabrafenib reduced by one dose level^g

- ^a. Pyrexia is defined as a body temperature equal to or above 38.5°C Celsius or 101.3°F Fahrenheit.
- ^b. For subjects experiencing pyrexia complicated by rigors, severe chills, etc., a clinical evaluation and laboratory work-up is mandatory for each event; anti-pyretic treatment should be started immediately at the first occurrence and prophylactic anti-pyretic treatment is recommended.
- ^c. Thorough clinical examination for signs and symptoms of infection or hypersensitivity is required; laboratory work up should include full blood count, electrolytes, creatinine, BUN, CRP, and liver function tests.
- ^d. Oral hydration should be encouraged in subjects without evidence of dehydration. Intravenous hydration is recommended in subjects experiencing pyrexia complicated by dehydration/hypotension.
- ^e. Anti-pyretic treatment may include acetaminophen (paracetamol), ibuprofen, or suitable anti-pyretic medication according to institutional standards. Prophylactic anti-pyretic treatment may be discontinued after three days in the absence of pyrexia
- ^f. In subjects experiencing pyrexia complicated by rigors, severe chills, etc., which cannot be controlled with anti-pyretic medication, oral corticosteroids should be started at the 2nd event and doses should be gradually increased for subsequent events.
- ^g. Dabrafenib should be reduced by one dose level after 3 episodes of pyrexia complicated by rigors, severe chills etc., which cannot be managed by best supportive care, including increasing doses of oral steroids. Re-escalation of dabrafenib is allowed if no episode of pyrexia is observed in the 4 weeks subsequent to dose reduction

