Pyrexia: In clinical studies, pyrexia was one of the most frequently occurring AEs (27%), most of which (64%) were considered to be related to study treatment. Events were primarily Grade 1 (55%) or Grade 2 (39%) in severity. The majority of events occurred early during study treatment, with a median time to onset of 1st occurrence of 3 weeks, and most cases (74% of first occurrences) were of short duration (≤5 days). The majority of subjects with pyrexia were managed without dose interruption or dose reduction. Across dabrafenib studies, all SAEs of pyrexia, influenza-like illness, cytokine release syndrome, and systemic inflammatory response syndrome underwent clinical review for the identification of serious non-infectious febrile events, with complications of severe rigors, hypotension, dehydration, or renal failure in the absence of another identifiable etiology (i.e., infection). Subjects should be evaluated for signs and symptoms of infection and work up considered as clinically indicated. Dabrafenib must be held for fever of 38.5C or higher, and blood samples for an absolute neutrophil count (ANC) and serum creatinine must be drawn in the setting of fever. Subjects with fever should have a medical evaluation including measurement of blood pressure. Cases of fever with severe rigors or fever with hypotension should be reported as SAEs (regardless of whether or not hospitalization was required).

Acute Renal Failure: Acute renal failure/renal failure has been rarely reported (<1%) in subjects receiving dabrafenib, and a case of granulomatous interstitial nephritis has also been reported in a clinical trial. In some cases complicated pyrexia may be associated with renal insufficiency/renal failure, possibly secondary to dehydration or hypotension. Renal function should be monitored carefully, especially in subjects with pyrexia. Dabrafenib should be interrupted in subjects with significantly elevated serum creatinine (creatinine rise >0.5 mg/dL [44 μmol/L] above baseline or creatinine >2.0 mg/dL [177 μmol/L]).

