3.7.4.2 Renal insufficiency

Cases of renal insufficiency have occurred in adult subjects receiving dabrafenib. Prior to start of study treatment, concomitant medications must be reviewed for the potential risk of inducing nephrotoxicity and concomitant medications may be modified if clinically possible.

Guidelines regarding management and dose reduction for renal insufficiency considered to be related to study treatment by the investigator are provided in [Table 3-5](#).

Table 3-5 Mandatory Dose Modification and Required Clinical Management Guidelines for Renal function alterations

For subjects with creatinine rise \geq 50% from baseline :	Required adverse event management guidelines	Mandatory dose modification requirements
1 st occurrence	
 ● If subject has fever: treat pyrexia as per Table 5 (please note NSAIDs can induce renal insufficiency, especially in subjects with dehydration); consider IV hydration ● Pediatric nephrology consult is recommended ● Re-check within 24 hours ● If creatinine rise is < 25% from baseline: ● Monitor creatinine weekly for 4 weeks to ensure levels remain within 25% of baseline ● If creatinine rise is \geq 25% but < 50% from baseline: 
 ● Monitor creatinine at least twice weekly, can decrease frequency if creatinine rise < 25% from baseline ● Avoid nephrotoxic agents ● If creatinine rise is \geq 50% but < 100% from baseline: 
 ● Monitor creatinine at least twice weekly ● Avoid nephrotoxic agents 	
 ● If creatinine rise is < 25% from baseline: Continue dabrafenib at current dose ● If creatinine rise is \geq 25% but < 50% from baseline: 
 ● Continue dabrafenib at current dose ● If creatinine rise is \geq 50% but < 100% from baseline: 
 ● Interrupt dabrafenib ● May restart dabrafenib at reduced dose if creatinine rise returns to < 25% from baseline ● If creatinine rise is \geq 100% from baseline, permanently discontinue dabrafenib
2nd occurrence	
 ● See guidance for first occurrence 	
 ● Permanently discontinue dabrafenib

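### The pyrexia guidance names ibuprofen as an optional anti-pyretic, including for fever with dehydration or hypotension, without the NSAID renal caution that the protocol gives only in Table 3-5

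*Protocol*

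**What the plan says.** Protocol Section 3.7.4.1 states that in the event of fever "the subject should be instructed to take anti-pyretics (e.g. ibuprofen or acetaminophen/paracetamol as appropriate to control fever". The first-event row of Table 3-4, in the column of recommended management, advises anti-pyretics as clinically indicated and asks the site to "initiate prophylactic treatment if associated with rigors, renal failure, dehydration, or hypotension". That bullet carries marker e, and footnote e says "Anti-pyretic treatment may include acetaminophen (paracetamol), ibuprofen, or suitable anti-pyretic medication according to institutional standards". The second-event row repeats the first-event guidance. No renal caution about NSAIDs appears in the section text, the table or its footnotes.

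The caution is in Section 3.7.4.2, Table 3-5: "please note NSAIDs can induce renal insufficiency, especially in subjects with dehydration". The same table, in its required-management column, also tells sites to keep away from nephrotoxic agents when the re-checked creatinine rise is 25% to under 50%, and again at 50% to under 100%. The table is headed for subjects whose creatinine has risen by at least 50% from baseline. Its lead-in limits it to "renal insufficiency considered to be related to study treatment by the investigator".

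Section 1.3 describes the renal risk of complicated fever: "In some cases complicated pyrexia may be associated with renal insufficiency/renal failure, possibly secondary to dehydration or hypotension".

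**The concern.** The protocol warns about NSAIDs in dehydration, but the warning is missing from the table that manages fever with dehydration. A site or family following the pyrexia guidance alone could choose ibuprofen in a state where the protocol itself says the class can cause renal insufficiency. The treatment is open-ended and given to children. Section 1.3 reports kidney findings in juvenile rats, and Amendment 3 raised the minimum age and added renal guidelines because of potential renal effects. What is at stake is an avoidable renal event in an individual patient.

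**Working it through.** The plan gives no figure to reproduce. The check is a comparison of texts, followed by a count of the patients who could still be affected.

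**Who reaches the caution.** Take a child with fever plus dehydration or hypotension.

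1. Creatinine up by at least 50% and judged treatment-related: Table 3-5 applies and the caution is reached. No gap.
2. Creatinine up by at least 50% but not judged treatment-related: the lead-in to Table 3-5 excludes the case. The caution is not reached.
3. Creatinine up by less than 50%: Table 3-5 is not entered. The caution is not reached.
4. Creatinine result not yet available: Table 3-5 cannot be entered. Footnote b of Table 3-4 asks for anti-pyretics to start at once in complicated fever, so the drug may come before the result. Footnote e lets prophylaxis stop after three fever-free days, so repeated doses are foreseen.

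**Whether other current text closes cases 2 to 4.**

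- Section 1.3 requires serum creatinine to be drawn when there is fever. Footnotes b and c of Table 3-4 make a laboratory work-up mandatory in complicated fever and list creatinine and BUN in it. These detect renal change; they do not steer the choice of anti-pyretic.
- Section 3.7.4.1 asks for careful renal monitoring in complicated fever, and footnote d recommends intravenous hydration. Neither mentions NSAIDs.
- Section 3.7.4.2 says "Prior to start of study treatment, concomitant medications must be reviewed for the potential risk of inducing nephrotoxicity". This review takes place before treatment, so it does not cover an anti-pyretic started later for a fever.
- Section 8.1 obliges the investigator to be told of any medication as soon as possible. That is notification, usually after the choice has been made.
- Tables 8-1 and 8-2 give no NSAID renal caution. Celecoxib is listed in Table 8-2 only as a drug that may lose efficacy.

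**Who is still reachable.** The inputs are the status paragraphs of the Amendment 10 and Amendment 11 rationales.

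- Treated: 85. Completed or discontinued: 52. Still on treatment: 85 − 52 = 33 at most.
- The count of 52 is identical at 06-Feb-2019 and 17-Jul-2020, so it may not have been updated and the true number may be lower.
- All 85 had already been treated by 06-Feb-2019. From then to 17-Jul-2020 is 365 + 162 = 527 days, or 527 / 30.4375 = 17.3 months. This is the minimum time since first dose for anyone still treated on that date.
- Section 3.7.4.1 says serious non-infectious febrile events "typically occurred within the first month of therapy". Every reachable patient is well past that period, although Table 3-4 provides for second and later fevers.

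The documents give neither the frequency of late complicated fever nor NSAID use, so no event count can be derived.

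**The case against.** The strongest reply is that footnote e is a general list of anti-pyretics for any fever, not advice to use ibuprofen in a dehydrated child. The wording is permissive, it defers to institutional practice, and it sits in a column of recommendations. Acetaminophen satisfies both tables. This stands, and it rules out calling the two tables contradictory, which a reader might infer from setting them side by side.

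A second reply is that safeguards surround the event: creatinine in fever, a mandatory work-up when the fever is complicated, renal monitoring, hydration, and reporting of all medication. This also stands in large part. A reader might infer from the 12-weekly chemistry schedule after Week 48 that a prescriber could be relying on a creatinine value up to 12 weeks old. The documents do not support that, because a fever itself triggers a draw. What remains is the interval before the result, and the child whose rise is below 50% or is not attributed to treatment.

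Third, the Study Procedures Manual and the Investigator's Brochure, to which Sections 3.7.3.1 and 3.7.2 refer, were not available and may contain the caution. This cannot be excluded.

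Fourth, the protocol's own note only cautions, so an instruction to avoid NSAIDs goes further. That is fair for the note itself. However, Table 3-5 already requires nephrotoxic agents to be avoided once it is entered, so the principle is the sponsor's own.

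**Conclusion.** The point holds as a minor patient-safety clarification. The pyrexia guidance permits an NSAID in a situation that includes dehydration, hypotension and renal failure, and omits a caution that the protocol states elsewhere. The gap is mainly doses given before the creatinine result, or with a rise below 50%; rises not judged treatment-related also fall outside Table 3-5.

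The size is small: at most 33 patients, all at least 17.3 months from first dose on 17-Jul-2020, and an unknown but probably low rate of complicated fever. A reader might infer an effect on dose-limiting toxicity counts or on dose finding. The documents give no basis for that as a consequence of the present text: Part 1 is closed, its doses are set, toxicity is assessed in the first 28 days, and enrollment has ended. No planned analysis is affected.

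The conclusion assumes that the status counts in the amendment rationales are upper bounds and that the manual and brochure do not already give the caution to sites.

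**What to change.** Add one sentence to footnote e of Table 3-4 and to the anti-pyretic sentence in Section 3.7.4.1, for example: *NSAIDs, including ibuprofen, may cause renal insufficiency, above all in dehydration; if fever comes with dehydration, hypotension or renal insufficiency, prefer acetaminophen/paracetamol and avoid NSAIDs (see Table 3-5).* Tell sites by a short note, since families receive fever instructions in advance.

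The cost is one sentence in two places. The downside is a narrower choice of anti-pyretic and more use of acetaminophen, which Section 12 asks sites to record when working up liver events. A child under liver monitoring would need a case-by-case decision.
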